## GOAL AND SPECIFIC AIMS

Aim 1: Compare the effectiveness of SSRF to usual care alone on traditional clinical metrics and patient-centered outcomes.

Aim 2: Evaluate for heterogeneity of treatment effect in high-risk subgroups.

Aim 3: Determine the impact of multiple rib fractures on post-discharge health status and time to return to work or usual physical activity.

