### **STATISTICS**

The primary and secondary outcomes will be analyzed on an intention to treat basis, though a per protocol analysis will also be performed. Demographics, injury characteristics, and eligible rib fracture patterns will be reported. Subgroup analyses will be stratified *a priori* by unit of admission. All statistical analyses will be performed using STATA® (version 15.1; StataCorp; College Station, TX) and R© (The R Foundation) commercially available software.

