### Frequentist Analysis

Generalized linear models (GLMs) will be used to analyze all outcomes and will include treatment group and unit of admission (stratifying variable) as covariates. For LOS outcomes, negative binomial or zero-inflated negative binomial (for outcomes with large number of zeros; *e.g.*, ventilator days, ICU days) regression models will be used. Binary outcomes will be analyzed with log binomial regression models to estimate relative risks (RRs). For longitudinal outcomes, we will use mixed models including treatment group, time, and center as covariates and a random intercept (and slope if needed) for subject. We will report RRs or group differences and 95% confidence intervals for all outcomes.

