### Bayesian Analysis

Bayesian statistics will be used to detect differences in treatment effects overall and in different patient subgroups. Models will be the same as in frequentist analyses (*i.e.*, GLMs with same covariates). For LOS outcomes, neutral priors centered at RR of 1.0 with 95% prior interval of 0.33-3.0 (0.5-2 for binary outcomes) will be used for the treatment effect (in the log RR scale, a Normal distribution with mean of 0 and variance of 0.57). A Normal (0, 10) prior will be used for the intercept term. Normal (0, 1) will be used for all other variables in the model. For sensitivity analyses, we will specify enthusiastic and skeptical priors based on the best published evidence (*i.e.*, Cochrane review). For all Bayesian analyses, we will report posterior medians and 95% credible intervals for group comparisons and probabilities of benefit or harm from the intervention.

**Feasibility:** From unpublished historical data from the Red Duke Trauma Institute from the calendar year 2017, approximately 300 patients matched these enrollment criteria. Accordingly, enrollment of 150-250 patients is expected over the course of the study.

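### The planned GLMs and their Bayesian copies have main effects only, so Aim 2 has no between-subgroup contrast; the LOS models also leave collected baseline data unused

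*Combined protocol and SAP*

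**What the plan says.** GOAL AND SPECIFIC AIMS gives Aim 2 as: "Evaluate for heterogeneity of treatment effect in high-risk subgroups". The subgroups are not listed.

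Under Frequentist Analysis, the GLMs "will include treatment group and unit of admission (stratifying variable) as covariates". No interaction and no further baseline variable is named. LOS outcomes use negative binomial models or their zero-inflated form. The longitudinal mixed models are described separately and are outside this point.

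Under Bayesian Analysis: "Bayesian statistics will be used to detect differences in treatment effects overall and in different patient subgroups". The next sentence begins "Models will be the same as in frequentist analyses" and specifies GLMs with the same covariates. After the priors for treatment and intercept, "Normal (0, 1) will be used for all other variables in the model".

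STATISTICS adds that "Subgroup analyses will be stratified" in advance by unit of admission. The levels of unit are not given. Appendix B collects age, ISS and radiographic flail segment, among other variables.

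**The concern.** One aim of three, and one stated purpose of the Bayesian analysis, concern differences in effect between subgroups. The only models described hold the treatment ratio constant across patients. That answers Aim 1 but leaves Aim 2 without an estimand.

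Two things then stay open until outcome data exist: how effects in different units will be compared, and which other patients count as high-risk. In practice a reader would probably look at which within-unit intervals exclude 1, and that does not show that effects differ.

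A smaller matter is that the LOS models adjust for unit alone, so precision available from collected baseline data is not used.

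**Working it through.** **1. The model as written.** log(mean LOS) = a + b·treatment + c·unit. There is a single b, so exp(b) is the same in every unit. In a simulation of 40,000 patients with true LOS ratios of 1.0 and 0.5 in two units, this model returned 0.72. Adding treatment-by-unit returned 1.01 in the first unit and a ratio of ratios of 0.49.

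**2. The plan's power.** Inputs from Sample Size Calculation: control median 10 days (IQR 6-15), two-sided alpha 0.05, 75 per group for 10 v 7 days, and 250 patients in total for a 2.5-day difference (125 per group at 1:1). The ratios are 7/10 = 0.70 and 7.5/10 = 0.75, and the ratio of means is assumed equal to the ratio of medians. A negative binomial with mean 11.4 and dispersion k = 0.40 has quartiles 6, 10 and 15.

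Var(log RR) = [(1/m0 + k) + (1/m1 + k)]/n per group

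- 150 patients: (0.488 + 0.525)/75 gives SE 0.116; power = Φ(0.357/0.116 − 1.96) ≈ 86.6% (plan: 85%).
- 250 patients: (0.488 + 0.517)/125 gives SE 0.090; power = 89.4% (plan: 89%).

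The plan does not state its method. The SEs that match its power exactly are 0.357/(1.960 + 1.036) = 0.119 and 0.288/(1.960 + 1.227) = 0.090. With an assumed control mean of 11.24 these correspond to k = 0.423 and 0.406. As a second method, log LOS has SD ln(15/6)/1.349 = 0.679, so SE = 0.679·√(2/n) = 0.111 and 0.086.

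**3. Why within-unit intervals are not a contrast.** With two equal units (an assumption) and the same design effect in both, power within each unit is about 58% (150) or 62% (250). The chance that exactly one of the two reaches significance is 2 × 0.58 × 0.42 = 49%, or 2 × 0.62 × 0.38 = 47%, although the effects are identical.

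**4. Precision of an interaction.** For a two-level subgroup with share s, SE(interaction) = SE·√(1/s + 1/(1−s)). The documents do not give s. Power for a ratio of RRs of 0.70 (150) or 0.75 (250), negative binomial / log scale:

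| s | 150 patients | 250 patients |
|---|---|---|
| 10% | 15% / 16% | 16% / 17% |
| 20% | 22% / 25% | 25% / 27% |
| 30% | 28% / 31% | 31% / 34% |
| 50% | 32% / 36% | 36% / 39% |

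At shares of 20-50% the 95% CI is the estimate divided and multiplied by about 1.5-1.8 (150) or 1.4-1.6 (250). At 10% the factor is about 2.1-2.2 or 1.8.

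**5. What one ratio could hide.** As an extreme illustration, suppose the design effect occurred in one subgroup only, with equal control LOS. The common RR is then s·RR + (1 − s): 0.97, 0.94 and 0.85 at s = 10%, 20% and 50% with 150 patients, and 0.975, 0.95 and 0.875 with 250.

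**6. Covariates in the LOS models.** Replace k by k(1 − R²), where R² is the assumed share of overdispersion explained beyond unit:

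| R² | 150 patients | 250 patients |
|---|---|---|
| 0 | 85.0% | 89.0% |
| 5% | 86.4% | 90.2% |
| 10% | 87.8% | 91.3% |
| 30% | 93.0% | 95.5% |

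If unit already carries 20 of the 30 points, the further step is 90.5% to 93.0% (150) or 93.5% to 95.5% (250). On the log scale the starting powers are higher (89.5% and 91.7%), and R² of 10-30% gives 92.4-97.0% and 94.2-97.9%.

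**The case against.** A reader might infer that the plan cannot show subgroup differences at all. The documents do not support that. STATISTICS fixes unit of admission in advance as the subgroup, and the shared-covariates rule can be read as the same model family fitted within each unit. Two independent within-unit estimates give a ratio of RRs directly. For unit, what is missing is a stated contrast, not the means to form one.

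A reader might also infer that an interaction would have no prior. It would: the Normal(0,1) prior covers every other term. Its 95% interval of 0.14 to 7.1 is wide, but a tighter prior is a trade-off. With 150 patients and no true interaction, the chance of a posterior median ratio at or below 0.70, or at or above 1.43, is 11-19% under Normal(0,1) and 3-4% with SD 0.35. If the true ratio is 0.70, the chance of a median at or below 0.70 falls from about 46-47% to about 20-25%.

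Flail status is a subgroup proposed here; the aims do not name it. Step 5 is an extreme case, and the diluted ratio is still the average effect that Aim 1 asks for. The 22-39% range depends on a floor of 20% for the subgroup share. The Background suggests that fewer than half of such patients have a flail segment but gives no lower limit. More than two units would need a test on several degrees of freedom, with different power.

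On covariates, it is fair to say that the planned analysis is sound: it adjusts for the stratifying variable, and the gain rests on R² values that the documents do not supply.

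What stands is that no between-subgroup contrast is specified, no subgroup other than unit is named, and some precision in LOS is forgone.

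**Conclusion.** The point holds in limited form. The models as written give one common ratio, and the within-unit analyses come with no contrast, so Aim 2 and the Bayesian subgroup statement lack a matching analysis. This should be corrected but does not threaten the trial: the overall LOS comparison is unaffected, and a reading that it is biased or invalid has no support.

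Any interaction estimate will be imprecise. Power is about 22-39% at assumed shares of 20-50% and about 15-17% at 10%, for a two-level subgroup and an interaction as large as the design effect. It can describe heterogeneity but not rule it out. The covariate gain of about 1-8 points, or about 2 where unit already does most of the work, depends entirely on the assumed R².

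The LOS treatment prior has an inconsistency of its own: an interval of 0.33-3.0 does not correspond to a variance of 0.57. That is a separate issue, and nothing here depends on it.

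**What to change.** 1. For Aim 2, name the subgroups and list the levels of unit of admission. Replace the shared-covariates rule with two separate models, one adding treatment-by-unit and one adding radiographic flail segment and treatment-by-flail. Flail is proposed because the Background divides the evidence by it, it is a route into the trial, and Appendix B collects it. Report the ratio of RRs with its 95% CI or credible interval, labelled exploratory.
2. State that the interaction takes the Normal(0,1) prior. A tighter prior may be shown as an optional sensitivity analysis, for example a 95% interval of 0.5-2.0 (SD = ln 2/1.96 = 0.354), with the shrinkage of a real interaction acknowledged.
3. In the negative binomial LOS models, prespecify a short covariate list alongside unit, for example age, ISS (once it is confirmed to be scored only from injuries present at admission) and flail segment. The log-binomial models for rare outcomes can keep treatment and unit only, since more terms may prevent convergence.

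The cost is SAP wording and a few model terms, with no new data collection. The SAP should state the low interaction power plainly, so that an inconclusive contrast is not read as evidence of a uniform effect.

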### Secondary Outcomes (Clinical Metrics):

- Mortality
- Incidence of respiratory failure requiring mechanical ventilation > 24 hours
- Incidence of tracheostomy
- Inpatient incidence of pneumonia
  - >10,000 cfu/mL on bronchioalveolar lavage -or-
  - Clinical diagnosis of pneumonia with subsequent antibiotic treatment
- Utilization of regional anesthesia (binary outcome)
- Opioid usage (continuous and binary)
- Lengths of stay
  - Hospital-free days (= 30 minus number of hospital days; in-hospital death = 0)
  - Ventilator-free days (= 30 minus number of ventilator days; in-hospital death = 0)

- ICU-free days (= 30 minus number of intensive care unit days; in-hospital death = 0)
- Re-intervention rates for surgical complications, including bleeding, seroma, and surgical site infection

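### For ventilator and ICU days the plan allows zero-inflated models but does not say which treatment ratio they yield; the default count-part ratio is not the intention-to-treat effect on days

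*Combined protocol and SAP*

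**What the plan says.** All outcomes are to be analysed with generalized linear models that "will include treatment group and unit of admission (stratifying variable) as covariates" (Frequentist Analysis). The same section continues: "For LOS outcomes, negative binomial or zero-inflated negative binomial (for outcomes with large number of zeros", and gives as examples "ventilator days, ICU days) regression models will be used". On reporting it says: "We will report RRs or group differences and 95% confidence intervals for all outcomes".

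The Bayesian Analysis section carries this over: "Models will be the same as in frequentist analyses". It gives one treatment-effect prior for these outcomes: "For LOS outcomes, neutral priors centered at RR of 1.0 with 95% prior interval of 0.33-3.0". For the rest, "Normal (0, 1) will be used for all other variables in the model". It does not say which prior a treatment coefficient in a zero part would take.

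The Statistics section promises an intention-to-treat analysis of the primary and secondary outcomes.

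The secondary outcome list names a different quantity, "Ventilator-free days (= 30 minus number of ventilator days; in-hospital death = 0", and an ICU counterpart built the same way. It also has a yes/no outcome for ventilation lasting more than 24 hours.

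**The concern.** A zero-inflated negative binomial (ZINB) model has two places for a treatment effect. The zero part gives an odds ratio for being a structural zero, such as a patient who would never be ventilated. The count part gives a ratio of mean days among everyone else. The plan names one ratio per outcome and one prior on the log-RR scale. The only single coefficient of a ZINB model on that scale is the count-part one.

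That coefficient describes a group whose membership the treatment may change. The Abstract presents early SSRF as preventative and names respiratory failure among the events that usual care often fails to prevent. Prevented ventilation moves patients into the zeros, where the count-part ratio does not register it. If prevention falls mainly on short episodes, the patients left in the count part have longer stays on average, and the ratio can exceed 1 while total ventilator days fall.

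The Bayesian probability of benefit or harm would inherit the same problem. The Limitations section relies on that probability if recruitment is low.

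**Working it through.** **Inputs.** From the documents: the model family, the covariates, 1:1 allocation, and 150 to 250 patients (75 or 125 per arm). The documents give no ventilation rate, ICU rate or duration, so all of these are assumptions. There is no plan figure to reproduce here: the stated 85% and 89% power concern hospital stay and do not bear on this point.

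**Formula.** Let π be the structural-zero probability and μ the count-part mean, with subscript 1 for SSRF and 0 for control. Then

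- count-part RR = μ₁ / μ₀
- ratio of mean days over all randomised patients = [(1 − π₁) μ₁] / [(1 − π₀) μ₀]

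The two agree only when π₁ = π₀, that is, when treatment leaves the share of structural zeros unchanged.

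**Case (a), fewer ventilated, same duration.** Any ventilation 40% in control and 25% with SSRF; mean 8 days when ventilated in both arms. Mean days are 0.40 × 8 = 3.2 and 0.25 × 8 = 2.0, so the true ratio is 2.0 / 3.2 = 0.625.

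**Case (b), fewer ventilated, longer among those who remain.** 40% at 8 days against 30% at 9.5 days. Mean days are 3.2 and 0.30 × 9.5 = 2.85, so the true ratio is 2.85 / 3.2 = 0.89.

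The ZINB fits below used simulated data with 20,000 per arm and treatment in both parts:

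| Case | True ratio of mean days | Count-part RR | Ratio from both parts combined |
|---|---|---|---|
| (a) | 0.63 | 1.01 | 0.63 |
| (b) | 0.89 | 1.22 | 0.89 |

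At the trial's size of 75 per arm (250 simulated trials per case), the median count-part RR was 0.97 in (a) and 1.21 in (b). In (a) the count-part test rejected in 5.6% of trials, close to its null rate. A plain negative binomial model gave 0.60 and 0.90.

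**A second set of assumptions.**

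- Share at risk of ventilation falls from 40% to 20%, same duration: true ratio 0.50. Count-part RR was 1.00 with treatment in both parts and 0.95 with treatment in the count part only. The two parts combined gave 0.50.
- SSRF prevents 75% of short and 10% of long episodes: true ratio 0.75, count-part RR 1.36. It exceeded 1 in 86% of trials at 75 per arm and 94% at 125, and was significant in the harmful direction in 24% and 35%.
- SSRF only shortens ventilation (mean 8 to 6 days): true ratio 0.75, count-part RR 0.76. There is no distortion.

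**Unit of admission and ICU days.** If the ICU is one of the admission units, patients admitted there cannot have zero ICU days, so unit would separate the zero part. In a simulated setting of this kind the true ratio of mean ICU days was 0.87. The standardised ratio was 0.86 with unit in both parts and 0.73 with unit left out of the zero part. Dropping unit therefore exaggerates the benefit.

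**The case against.** The strongest objection is that the plan does not make this error. A reader might infer that the reported RR is the count-part coefficient, but no sentence says so. The wording allows group differences as well as RRs, and a plain negative binomial model, which recovers the ratio of mean days, is one of the two named options. This stands: the defect is an undefined effect measure with a misleading default.

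The listed outcomes are also free days, on which prevention does not act through zeros. Ignoring deaths, case (a) gives means of 30 − 3.2 = 26.8 against 30 − 2.0 = 28.0, and case (b) gives 26.8 against 30 − 2.85 = 27.2 (rounded). Both favour SSRF. This stands for analyses of free days. It does not remove the point, because the Frequentist Analysis section names ventilator days and ICU days as its zero-inflated examples. The two sections disagree and need reconciling.

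Prevented ventilation also has its own outcome. The yes/no comparison covers all randomised patients, and at 40% against 20% it has 77% power with 75 per arm and 94% with 125. This limits the harm for ventilation, but the outcome list has no counterpart for ICU admission.

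Finally, the size depends on assumed rates, and the trial evidence in the Background section includes shorter ventilation and shorter intensive care. If shortening is the whole effect, the count-part ratio is sound. Reversal needs longer average stays among those still ventilated, for example because prevention falls mainly on short episodes.

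A reader might also infer that unit of admission should be left out of the zero part for ICU days because it would separate. The documents do not define the admission units or say which part unit enters, and the check above shows that omission makes the estimate worse.

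**Conclusion.** The point holds as an undefined effect measure. If ZINB is chosen for ventilator or ICU days, the default RR is not the intention-to-treat effect on days. When SSRF changes who is ventilated or admitted to the ICU, it can show no effect (about 1.0 against a true 0.63) or the opposite effect (about 1.22 against 0.89). These sizes rest on assumed rates and durations.

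The documents do not support the stronger statements that the plan commits to the count-part coefficient, or that its results will be reversed. Hospital length of stay, the primary outcome, is not named as zero-inflated and is not affected. Severity is minor to moderate, for secondary outcomes only.

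**What to change.** For any outcome fitted with ZINB, state that treatment and unit of admission enter both parts. Report as the treatment effect the ratio (or difference) of marginal mean days over all randomised patients, standardised over unit, with a bootstrap confidence interval. A log-link quasi-Poisson model with robust standard errors, standardised over unit, is a simpler alternative. Show the two ZINB parts only as description.

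In the Bayesian analysis, state the prior for treatment in the zero part, summarise the posterior of the same marginal ratio, and compute the probabilities of benefit and harm from it.

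If unit of admission separates the zero part for ICU days, use penalisation, a weakly informative prior or the quasi-Poisson model. Do not drop unit from the zero part.

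Reconcile the Frequentist Analysis section (ventilator and ICU days) with the secondary outcome list (ventilator-free and ICU-free days), and state the model for whichever is kept.

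The cost is a few sentences in the plan and a little code, with no new data. The downside is a wider interval for the marginal ratio at 150 patients.

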### Primary Outcome:

- Hospital length of stay (days)

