### Randomization:

Eligible subjects who have consented to participate will be randomized into one of two groups: 1) Control arm or 2) Intervention arm. The two arms are described in detail below. A 1:1 allocation ratio using a permuted block design of 4 or 6 will be used to ensure equal number of patients in each group. Randomization will be performed using the randomization module in REDCap and stratified by unit of admission.

Control Arm: Control patients will receive usual care per our established institutional guidelines, consisting of pulmonary toilet, lung volume expansion exercises, and a multimodal approach to oral pain medication management. For severe pain not responding to oral therapy, intravenous narcotics, lidocaine, or ketamine may be added. Regional analgesia techniques such as epidural analgesia, paravertebral analgesia, and intercostal nerve blockade may also be considered. The pain medication regimen is deescalated as pulmonary status and pain control allow.

(<https://med.uth.edu/surgery/files/2017/06/Chest-Management-of-Multiple-Rib-Fractures-2013.pdf>)

For patients who fail all of these therapies and desire to proceed with SSRF, the procedure may be offered late, as salvage therapy.

Intervention Arm: The intervention will consist of early surgical stabilization of the fractured ribs plus usual care. If randomized to SSRF, the procedure should occur as early as possible (given the patient clinical status and need for more emergent procedures), ideally within the first 72 hours of hospital admission. Since stabilization of all fractures may not be possible due to anatomic exposure (e.g., the first, second, and third ribs may be difficult to access due to their location), the surgery must stabilize at least one true rib (ribs 1-7). Stabilization of the true ribs is considered more critical due to their greater contribution to chest wall volume and mechanical respiratory function.

Observation Arm: Patients refusing consent to randomization will be invited to participate in the observational arm. Patients selecting this option will be asked to complete the same assessments as the randomized groups.

Equipment: In order to maintain a pragmatic approach, surgical stabilization will be performed using any commercially available internal rib fixation system, at the discretion of the operating surgeon.

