### Sample Size Calculation

We expect to enroll 150-250 total patients. We calculated the effect size we will be able to detect in hospital LOS, assuming a median LOS of 10 days (IQR 6-15) in the control group and two-sided alpha of 0.05. A sample size of 150 patients (75 per group) will provide 85% power to detect a difference of 3 days (*i.e.*, median LOS of 7 days in intervention group). With a sample size of 250 patients, we will have 89% power to detect a difference of 2.5 days in hospital LOS.

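### The primary length-of-stay analysis names no variance estimator; with default negative binomial standard errors the 5% test may be liberal if stays are uncapped and long-tailed

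*Combined protocol and SAP*

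**What the plan says.** The Primary Outcome section gives hospital stay in days, with no cap and no transformation. The Frequentist Analysis section assigns "For LOS outcomes, negative binomial or zero-inflated negative binomial" models to stay outcomes, the zero-inflated form being for outcomes with many zeros, such as ventilator or ICU days. Treatment group and unit of admission are covariates, and 95% confidence intervals are promised. The section does not mention model-based, robust, bootstrap or permutation inference, a check of model fit, or an alternative analysis of LOS. The Bayesian Analysis section reuses the same models, and its sensitivity analyses vary only the priors.

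The Sample Size Calculation section works from "assuming a median LOS of 10 days (IQR 6-15) in the control group and two-sided alpha of 0.05" and states: "A sample size of 150 patients (75 per group) will provide 85% power to detect a difference of 3 days"; "With a sample size of 250 patients, we will have 89% power to detect a difference of 2.5 days in hospital LOS". It names no test.

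The Data Collection section ends in-hospital data collection at discharge or day 30, whichever is sooner. The 30-day scale is explicit only for the secondary free-day outcomes. Appendix B lists discharge date and time and hospital days without a limit.

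**The concern.** The maximum likelihood dispersion of an NB model is fitted to the whole shape of the data, mostly the bulk of ordinary stays. A few very long stays raise the true variance of the estimated mean ratio by more than that dispersion reflects, so the model-based standard error is too small. The primary confidence interval is then too narrow, and a chance imbalance in long stays can look like an effect in either direction. Very long stays are plausible in this population: eligibility extends to flail segment, outcomes include prolonged ventilation and tracheostomy, and Appendix B lists long-term acute care among discharge dispositions. At stake is the nominal "two-sided alpha of 0.05" for the single primary test.

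**Working it through.** **Inputs from the plan.** Control median 10 and quartiles 6 and 15; 75 per group (150 total) or, with the 1:1 allocation, 125 per group (250 total); two-sided 5%; NB model. **Assumed:** the tail beyond the upper quartile, because the plan gives nothing there.

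**1. The plan's power figures.** An NB with mean 11.2 and dispersion k = 0.38 has quartiles of exactly 6, 10 and 15. NB Wald power uses var(log RR) = [(1/m1 + k) + (1/m0 + k)]/n. I take m0 = 11.2 and k = 0.40.
- 75 per group, ratio 0.70 (m1 = 7.84): var = (0.0893 + 0.1276 + 0.80)/75 = 0.01356, SE = 0.1164, z = 0.3567/0.1164 = 3.063, power = Φ(3.063 − 1.96) = 86.5% (stated 85%).
- 125 per group, ratio 0.75 (m1 = 8.4): var = (0.0893 + 0.1190 + 0.80)/125 = 0.00807, SE = 0.0898, z = 3.203, power = 89.3% (stated 89%).

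With k = 0.42 the pair is 85.2% and 88.1%. The stated figures are therefore consistent with an NB.

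**2. The mechanism, by hand, for a log-normal.** The log-SD from the quartile ratio is ln(15/6)/(2 × 0.6745) = 0.679. The implied quartiles are 10·exp(±0.458) = 6.3 and 15.8, and the mean is 10·exp(0.679²/2) = 12.59.
- True squared coefficient of variation: exp(0.679²) − 1 = 0.586.
- What the NB fit assumes: 1/12.59 + fitted k of 0.349 = 0.428.
- Model SE at 75 per group: √(2 × 0.428/75) = 0.107. Approximate true SE: √(2 × 0.586/75) = 0.125 (simulated 0.123).
- Real size of the test: 2[1 − Φ(1.96 × √(0.428/0.586))] = 2[1 − Φ(1.675)] = 9.4%.

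The ratio of the two SEs does not involve n, so a larger trial does not remove the error.

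**3. Simulation.** Both arms have the same distribution, stays are whole days, and the NB is fitted by maximum likelihood. The table gives type I error at nominal 5%, as model-based / robust (HC1 sandwich). There were 12,000 replicates per cell (6,000 in rows marked *), treatment the only covariate.

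| Assumed LOS | 75 per group | 125 per group |
|---|---|---|
| NB, mean 11.2, k 0.38 | 5.4% / 5.3% | 4.9% / 4.9% |
| Log-normal, log-SD 0.679 | 9.7% / 5.8% | 9.3% / 5.6% |
| Log-normal, log-SD 0.757 (lower quartile matched) | 10.9% / 5.8% | 10.4% / 5.4% |
| Gamma plus 5% of stays, median 40 days | 9.8% / 5.8% | 9.5% / 5.1% |
| Gamma plus 3% of stays, median 60 days | 13.7% / 6.4% | 13.3% / 5.6% |
| Log-normal 0.679, cut at 30 days | 5.9% / 5.1% | 5.7% / 5.0% |
| 3% near 60 days, cut at 30 days* | 5.9% / 5.4% | 6.0% / 5.6% |

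Separate runs of the case with 3% near 60 days gave 11-12% and 13-13.4% model-based, with quartiles still 6, 10 and 15. Two per cent of stays near 40 days gave 7.5%. Six per cent of stays between 30 and 90 days gave 15.1%, against 6.7% robust.

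**4. With the planned unit covariate.** This assumes two units with medians 8 and 14 days and 40% of patients in the longer-stay unit (2,000 replicates, Monte Carlo SE about 0.5 points).

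| Assumed LOS within unit | 75 per group | 125 per group |
|---|---|---|
| NB | 6.4% / 6.2% | 5.2% / 5.1% |
| Log-normal, residual log-SD 0.6 | 8.2% / 6.3% | 7.7% / 5.7% |
| Log-normal, residual log-SD 0.8 | 11.2% / 6.8% | 10.7% / 5.0% |
| Log-normal 0.6, cut at 30 days | 6.6% / 5.7% | 6.4% / 5.3% |

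**The case against.** A reader might infer that the plan has chosen model-based standard errors and that its primary test therefore rejects 9-15% of the time under no effect. The documents do not support that, for four reasons.

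- **No estimator is named.** Robust errors would be compatible with the text as written. The gap is an unspecified detail, and the inflation follows only if the usual default is used.
- **The stated quartiles favour the NB.** An NB reproduces 6, 10 and 15 exactly; the log-normal gives 6.3, 10 and 15.8. On the log scale the lower half implies an SD of ln(10/6)/0.6745 = 0.76 and the upper half ln(15/10)/0.6745 = 0.60, a lean away from log-normal. The power figures also fit an NB. But quartiles say nothing about the top few per cent, and an NB bulk with 3% of stays near 60 days has the same quartiles.
- **The tail is assumed.** No section gives a proportion of long stays. Adjusting for unit can bring the log-normal case to about 8%, although a wider residual spread gives about 11%.
- **The 30-day limit may remove the problem.** If the Data Collection limit cuts primary LOS at day 30, the error is about 5-6.6%. The documents do not say whether it does, and the uncapped outcome definition and the discharge date in Appendix B leave it open.

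All four stand as limits on size. None argues against the remedy, which is valid with or without a cap. It is also fair that sandwich errors are imperfect: they gave 6-7% in the heavier tails and 7.3% in one extreme case at 75 per group.

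**Conclusion.** The point holds in conditional form. The plan leaves the variance estimator of its primary test unstated and provides no analysis that would protect the test if the NB variance is wrong. With default errors, the 5% level is kept to within about 1.6 points if LOS is NB or cut at 30 days. If LOS is uncapped with a longer tail, which "assuming a median LOS of 10 days (IQR 6-15) in the control group" does not rule out, type I error is roughly 6-15%. The upper figure is not a strict ceiling: a quartile-matched log-logistic, a very heavy tail, gave 17-18%. The size rests on the assumed tail, on default standard errors being used, and on the unresolved 30-day question. The case for change is that better protection is nearly free, not that the planned test has been shown to fail.

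**What to change.** In the Frequentist Analysis section:

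1. State that the primary LOS p-value and 95% confidence interval come from robust (sandwich) standard errors on the NB model with treatment and unit of admission.
2. Add a permutation p-value, with treatment labels permuted within unit of admission, as a supporting check, because sandwich errors can remain slightly liberal in extreme tails.
3. State whether primary LOS is cut at 30 days, and reconcile the Primary Outcome, Data Collection and Appendix B text accordingly.

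The first change is one software option, for example vce(robust) in Stata, which the plan already names. The point estimate is unchanged. If the NB holds, the cost is negligible. If the tail is log-normal, intervals widen slightly, and power at 75 per group for a 30% reduction is about Φ(0.357/0.123 − 1.96) = Φ(0.94) = 83%, against the stated 85%.
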